2.0 Objectives*

- Explore Adjunctive acupuncture effect on QOL and quantitative measures for Chronic COPD patient undergoing pulmonary rehab.
- Explore the dose response relationship between adjunctive acupuncture and improvement in pulmonary function and/or quality of life.
- Explore the effect of EA on inflammatory markers in patients undergoing PR Hypotheses
- EA will: will significantly improve QOL and quantitative measures for Chronic COPD patient undergoing pulmonary rehab.
- There will be a significant dose response relationship between adjunctive acupuncture and improvement in pulmonary function and/or quality of life.
- EA will significantly reduce inflammatory markers in patients undergoing PR

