4.0 Study Endpoints*

Pulmonary function as measured by:

- PFTs: FEV1, FEV1%, FVC, FVC%

Inflammation as measured by:

- Blood Eosinophils, Neutrophil, CRP

Quality of life as measured by:

- Dyspnea scores (31): Borg
- HRQOL
 - St George's Respiratory Questionnaire
 - PH Q9
- 6-minute walk distance

PROTOCOL TITLE: Exploring the Dose-Response Effect of Adjunctive Acupuncture on Pulmonary Rehabilitation: A Pilot Study

- The incidence of Acute Exacerbations (AE)

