6.0 Procedures Involved*

The study will use a wait-time control design with varying intervention durations, i.e., dose.

Group	
A	INTERVENTION- 8 weeks acupuncture
B	INTERVENTION- 4 week acupuncture
C	SOC CONTROL- standard of care for the study duration

PROTOCOL TITLE: Exploring the Dose-Response Effect of Adjunctive Acupuncture on Pulmonary Rehabilitation: A Pilot Study

Patients will be recruited from the DHMC pulmonary rehab program. They will be randomized to start in group A or B with groups A and B to the EA intervention of 4 or 8 weeks or will volunteer to be a control subject in group C.

Current practice at the DHMC pulmonary rehabilitation unit is 6 - 12 patient per rehab cohort. Their program is applied in 4- or 8- week increments.

As this is a pilot, part of the study is to evaluate the facilitators and barriers to recruitment. For example, this protocol can be extended in time if recruitment is slow. We will be aiming for at least 10 participants per arm. If recruitment is robust, we will cap each arm at 30 participants.

Intervention: DHMC pulmonary rehabilitation program + EA Lung Mu-Shu+ St36
Control: DHMC pulmonary rehabilitation program

EA intervention will be applied sitting for 20 minutes prior to pulmonary rehab session.

Analysis

The blinded data will be submitted to Dartmouth Synergy Clinical and Translational Science Institute, Biostatistics Consultation core for independent statistical analysis.

Descriptive analysis of continuous variables will include median and interquartile range (IQR), or mean and standard deviation (SD) as appropriate. Categorical variables will be reported as counts and percentages. Baseline characteristics will be compared across all 3 groups using Chi-square test or Fisher's exact test where appropriate for categorical variables and t-test for continuous variables for all enrolled participants.

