Predictors of change in scores compared with baseline for outcomes each follow-up will be selected via stepwise general linear models with an inclusion criterion of $P < 0.1$ to enter and $P > 0.05$ to exit, while age and gender will be forced in the models. In addition, age, gender, and baseline outcomes will be included in all longitudinal outcome models. Outcomes analyses using changes from baseline at each follow-up, with a mixed-effects longitudinal regression model including a random individual effect to account for correlation between repeated measurements within individuals. Computations will be performed using SAS procedure PROC MIXED (SAS version 9.4, SAS Institute Inc., Cary, NC) or its equivalent. Statistical significance was defined as $p < 0.05$ based on a two-sided hypothesis test with no adjustments made for multiple comparisons.

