17.0 Data Management* and Confidentiality

The blinded data will be submitted to Dartmouth Synergy Clinical and Translational Science Institute, Biostatistics Consultation core for independent statistical analysis.

Descriptive analysis of continuous variables will include median and interquartile range (IQR), or mean and standard deviation (SD) as appropriate. Categorical variables will be reported as counts and percentages. Baseline characteristics will be compared across all 3 groups using Chi-square test or Fisher's exact test where

PROTOCOL TITLE: Exploring the Dose-Response Effect of Adjunctive Acupuncture on Pulmonary Rehabilitation: A Pilot Study

appropriate for categorical variables and t-test for continuous variables for all enrolled participants.

Predictors of change in scores compared with baseline for outcomes each follow-up will be selected via stepwise general linear models with an inclusion criterion of $P < 0.1$ to enter and $P > 0.05$ to exit, while age and gender will be forced in the models. In addition, age, gender, and baseline outcomes will be included in all longitudinal outcome models. Outcomes analyses using changes from baseline at each follow-up, with a mixed-effects longitudinal regression model including a random individual effect to account for correlation between repeated measurements within individuals. Computations will be performed using SAS procedure PROC MIXED (SAS version 9.4, SAS Institute Inc., Cary, NC) or its equivalent. Statistical significance was defined as $p < 0.05$ based on a two-sided hypothesis test with no adjustments made for multiple comparisons.

This is a pilot study so power analysis is not applicable.

All collected data will be anonymized and stored on password protected hard drives behind the hospitals firewall. Only the PI or his designee will be allowed access to the data. At the end of the study all key tables mapping identifiable data to unique identifiers will be erased. All data will be kept in compliance with DHMC data policies.

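### The outcome models name no treatment, dose or visit term, so the tests of the EA and dose-response hypotheses are undefined; a prespecified model with visit-specific contrasts, kept apart from stepwise selection, should define them.

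*Combined protocol and SAP*

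**What the plan says.** Section 2.0 hypothesises that EA "will significantly improve QOL and quantitative measures for Chronic COPD patient undergoing pulmonary rehab". It also states: "There will be a significant dose response relationship between adjunctive acupuncture and improvement in pulmonary function", with quality of life as a further or alternative outcome. A third hypothesis is a significant fall in inflammatory markers.

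The outcome analysis stands in Section 6.0 (Analysis) and is repeated in Section 17.0. It has two parts:

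- Predictors of change at each follow-up are "selected via stepwise general linear models with an inclusion criterion" of P < 0.1 and an exit criterion of P > 0.05. Age and gender are forced in. No list of candidates is given.
- The longitudinal part reads "Outcomes analyses using changes from baseline at each follow-up", using a "mixed-effects longitudinal regression model including a random individual effect". For covariates, "age, gender, and baseline outcomes will be included in all longitudinal outcome models".

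Significance is two-sided p < 0.05 with no multiplicity adjustment. In the analysis text, group is used only to compare baseline characteristics.

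On design, Sections 6.0 and 9.0 give A 8 weeks of EA, B a 4-week wait and then 4 weeks of EA, and C none. Patients are randomised between A and B, or "will volunteer to be a control subject in group C". The Section 9.0 text sets assessments at T0, T4, T8 and T9, the last two being 3 and 6 months after the intervention. Section 4.0 lists 11 continuous measures and the incidence of acute exacerbations.

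**The concern.** The hypotheses concern a treatment effect and a dose effect, but the analysis text names no term that carries either one. The analyst would have to supply it, and the obvious candidates answer different questions:

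- Group as one of the stepwise candidates. Only age and gender are protected, so group can be dropped.
- One group term averaged over visits. This pools EA versus no EA with 8 versus 4 weeks.
- A linear term in weeks of EA. This brings in group C, which is not randomised.

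The plan also does not say whether the stepwise picks enter the mixed model. Acute exacerbations are an incidence and have no change score, so the stated model does not cover them. At stake is whether a p-value below 0.05 can be tied to a comparison fixed before the data were seen.

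**Working it through.** The plan gives no power, effect size or SD, so there is no figure of its own to reproduce. Effects below are in SD units, and the 0.5 SD effect is an assumption.

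**1. Terms named.** The written model has an intercept, age, gender and baseline value: 4 fixed-effect columns, none for treatment or visit.

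**2. What each contrast means.** Cumulative weeks of EA, from Sections 6.0 and 9.0:

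| Group | T4 | T8 | T9 |
|---|---|---|---|
| A | 4 | 8 | 8 |
| B | 0 | 4 | 4 |
| C | 0 | 0 | 0 |

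A minus B is therefore EA versus no EA at T4 (if B is assessed before its first session) and 8 versus 4 weeks at T8 and T9. No assessment is listed at week 8, so the second contrast is seen only 3 and 6 months after treatment.

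**3. One averaged group term.** Let A minus B be 0.5 SD at T4 and d at T8 and T9. The average is (0.5 + 2d)/3:

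- d = 0: 0.5/3 = 0.17 SD
- d = 0.25: 1.0/3 = 0.33 SD
- d = 0.5: 1.5/3 = 0.50 SD

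The same T4 effect is reported as anything from 0.17 to 0.50 SD.

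**4. Group left to stepwise selection.** This was simulated under the stated rule (enter P < 0.1, exit P > 0.05, age and gender forced), for A versus B with 10 per arm, 5 or 10 pure-noise candidates, normal errors and 2,000 runs per setting.

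| True effect | Group kept | Mean estimate when kept |
|---|---|---|
| 0 | 5–6% | about 0 |
| 0.5 SD | about 16% | 1.15–1.18 SD |
| 0.8 SD | 34–35% | 1.27–1.30 SD |

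With group always in the model, the mean estimates were about 0.50 and 0.80 SD. The harm is omission and exaggeration (1.15/0.5 = 2.3 times the assumed truth), not false positives.

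**5. Stepwise picks fed into the mixed model.** These are type I error rates for A minus B at T4, with 10 per arm, within-patient correlation 0.5 and 5, 10 or 20 noise candidates (3,000 runs per setting):

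- prespecified model: 4.6–5.2%
- group added after selection: 4.7–5.2%
- group forced in during selection: 6.4%, 7.5% and 9.3%

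A simpler single-visit check of the last case (1,500 runs) gave 5.5%, 5.4% and 12.3%. Inflation is clear only with many candidates.

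**6. Dose trend.** With fixed doses 8, 4, 0 and n = 10 per arm, the mean dose is 4 and Sxx = 10 × (16 + 0 + 16) = 320. The weight on each group mean, per 8 weeks, is 8 × 10 × (dose − 4)/320, giving A +1, B 0, C −1. The trend is then A minus C.

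With cumulative dose by visit (table in step 2), visit effects, correlation 0.5 and equal arms, the generalised least squares weights at T4, T8 and T9 are:

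- A: 0, 0.44, 0.44
- B: −0.33, 0.11, 0.11
- C: 0.33, −0.56, −0.56

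C's weights sum to −0.78, so a 0.5 SD difference in C unrelated to EA moves the trend by 0.5 × 0.78 = 0.39 SD, against 0.5 SD with fixed doses.

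**7. Precision of a full model.** Columns: 1 intercept + 3 covariates + 2 group + 2 visit + 4 interaction = 12. An unadjusted A minus B at one visit with 10 per arm has 95% CI half-width 2.101 × √(2/10) = 0.94 SD; the simulated mixed model gave 0.93–0.94 SD. The difference detectable with 80% power is 1.33 SD (t-based).

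**The case against.** The best defence is that the plan lists adjusting covariates and does not claim to list the whole model. Group may be taken for granted, and analysing change at each follow-up points to results by visit. That much stands: a reader might infer that the planned model is incapable of testing EA, but the documents show only that the treatment term and contrasts are unspecified. It does not close the gap, because nothing says whether group is forced or selectable, averaged or by visit, categorical or linear in weeks.

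Three other strong readings are also unsupported.

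- *Stepwise selection will inflate type I error.* The plan gives no candidate list and no link from the picks to the mixed model. Two of the three arrangements in step 5 are about nominal.
- *The dose trend rests wholly on A versus C.* This holds only for fixed doses and equal arms. With cumulative dose by visit, B contributes, although C still weighs heavily.
- *B and C are not assessed at T8 and T9.* The Section 9.0 table shows entries in those columns for A only, but the text there says patients are assessed at both visits, and a merged cell may have been lost in extraction. This needs confirming and is not a finding.

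Pilot status is a fair answer to low power. It is not an answer to an unstated comparison when the plan sets hypotheses of significance at p < 0.05. The objection that a 12-column model is heavy for about 30 patients is right and shapes the fix.

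**Conclusion.** The point holds as a specification gap that should be fixed. The plan does not define the treatment or dose test for its own hypotheses, and its only stated rule for choosing predictors would allow treatment to be dropped.

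The firm parts need no assumption: the terms named, the change in meaning of A minus B between T4 and the later visits, and the volunteer status of C. The sizes are conditional. Retention in about 16% of trials with a mean estimate of about 1.15 SD assumes a true 0.5 SD, 10 per arm and group left to selection. The 0.17 to 0.50 SD range assumes one averaged group term.

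The 10-per-arm figures fit the total of 30 in Sections 1.0 and 12.0. Results at 30 per arm would apply only if the cap in Section 6.0 governs. The three-group baseline t-test and the entry and exit thresholds are minor and form no part of this conclusion.

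**What to change.** In Sections 6.0 and 17.0:

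1. Take no treatment estimate or p-value from stepwise selection. Label any predictor search exploratory.
2. For each continuous outcome, prespecify change from baseline = group + visit + group × visit + baseline value + age + gender, with a random patient effect.
3. Report the randomised A minus B contrast with 95% confidence intervals at T4 (EA versus no EA, with B assessed before its first session) and at T8 and T9 (8 versus 4 weeks, 3 and 6 months after treatment). Put the weight on estimates: 11 measures × 3 visits give 33 unadjusted contrasts.
4. Report contrasts with C, and any 0/4/8-week trend that uses C, separately and as non-randomised.
5. Analyse acute exacerbations with a count or rate model (Poisson or negative binomial) with log follow-up time as offset, since Section 14.0 censors patients who leave. Split follow-up at T4 so that the two treatment comparisons are not pooled.
6. Confirm that B and C are assessed at T8 and T9, as the Section 9.0 text says, and state at which visits the blood markers are taken.

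The cost is wording, with no new functional or quality-of-life assessments if the Section 9.0 text is right. If only A is assessed at T8 and T9, either those assessments are added or the 8-versus-4-week contrast cannot be reported. The predictor search becomes exploratory. The change defines the comparisons but adds no power.

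### Exploratory objectives are paired with hypotheses worded as significance claims, tested unadjusted at 0.05 on 12 unranked measures with no primary test, so the false-claim risk is well above 5%

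*Combined protocol and SAP*

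**What the plan says.** Section 1.0 separates a primary objective (quality of life and quantitative measures) from secondary ones (dose response, inflammatory markers). Section 2.0 frames all three as exploration, then states three hypotheses that each predict a significant result. The second reads: "There will be a significant dose response relationship between adjunctive acupuncture and improvement in pulmonary function and/or quality of life". The first joins quality of life and quantitative measures with a plain 'and'; the third refers to inflammatory markers in the plural.

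Section 4.0 lists measures under pulmonary function, inflammation and quality of life, and marks none as primary.

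Section 9.0 sets assessments at T0, T4, T8 and T9, for functional and quality-of-life measures only. Section 6.0 (Analysis) models change from baseline at each follow-up with a mixed model in a three-group study and names no contrast. It defines significance as two-sided p < 0.05 "with no adjustments made for multiple comparisons". Section 17.0 repeats the rule. Sections 12.0 and 17.0 say that sample-size and power calculations do not apply because this is a pilot.

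**The concern.** The plan has a rule for declaring significance and hypotheses worded to be settled by it, but it does not say which test settles them. For the dose-response hypothesis the problem is explicit: a result in either of two domains is enough, each domain holds several measures, and there is more than one visit. With no true effect, the chance that some comparison crosses 0.05 is therefore well above the nominal 5%. At stake is how the results are described. Section 8.0 sends them to subjects, providers and the public, and a reader could not tell which p-value was meant to count.

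**Working it through.** The plan states no familywise error rate, so there is no figure of its own to reproduce. The check is a count followed by a range.

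**Measures (Section 4.0).** Pulmonary function, 4 ("PFTs: FEV1, FEV1%, FVC, FVC"%); inflammation, 3 ("Blood Eosinophils, Neutrophil, CRP"); dyspnoea, 1 ("Dyspnea scores (31): Borg"); questionnaires, 2 ("St George's Respiratory Questionnaire" and PHQ-9); walk distance, 1; exacerbations, 1. Total 4 + 3 + 1 + 2 + 1 + 1 = 12.

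**Measures with stated visits (Section 9.0).** I take the functional and quality-of-life set to be the 4 pulmonary function measures, Borg, SGRQ, PHQ-9 and walk distance: 8. Inflammatory markers have no stated visits, and exacerbation incidence is not naturally a change from baseline.

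**Visits and contrasts.** Three post-baseline visits (T4, T8, T9). Three groups allow at most three pairwise contrasts; these are inferred, not stated.

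**Formulas.** With m independent tests and no true effect:
- expected false positives = 0.05 × m
- chance of at least one = 1 − 0.95^m
- chance of at least one favouring electro-acupuncture (EA) = 1 − 0.975^m, since half of the two-sided 0.05 lies on each side

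| Reading of the plan | m | Expected | At least one | At least one false benefit |
|---|---|---|---|---|
| One group test per measure | 12 | 0.6 | 46.0% | 26% |
| 8 scheduled measures × 3 visits | 24 | 1.2 | 70.8% | 46% |
| 12 measures × 3 visits | 36 | 1.8 | 84.2% | 60% |
| 8 × 3 × 3 contrasts | 72 | 3.6 | 97.5% | 84% |
| 12 × 3 × 3 (upper bound) | 108 | 5.4 | 99.6% | 94% |

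**Correlated tests.** The tests are not independent, and the documents give no correlations. I simulated the case of no effect (40,000 runs, three equal groups, normal test statistics), assuming equal correlation between measures and a correlation between visits of 0.5 or 0.8. Pairwise contrasts were formed from the same three groups, so their dependence is included. Chance of at least one false positive, in either direction:

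| Assumed correlation between measures | 12 tests | 36 tests | 108 tests |
|---|---|---|---|
| 0.3 to 0.7 | 23% to 40% | 40% to 73% | 71% to 96% |
| 0.9 | 13% to 14% | 24% to 31% | 48% to 59% |

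Even the lowest figure, 13%, is more than twice 5%. The stepwise selection of predictors (p < 0.1 to enter, Section 6.0) adds further unadjusted tests, which are not counted here.

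**The case against.** The strongest reply is that this is an exploratory pilot that openly says it does not adjust. The title, the objectives and the absence of a power calculation all point that way, and disclosed non-adjustment in such a study is largely a matter of preference. That stands: lack of adjustment alone would not be a flaw. But disclosure does not tell a reader which p-value decides a hypothesis, and pilot status does not reconcile exploratory objectives with predictions of significance.

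Several stronger readings are tempting, and the documents do not support them.
- *The trial is confirmatory.* The documents never say so.
- *There will be 108 tests and a 99.6% error rate.* That count is a maximum: the visit schedule covers only some measures and no contrasts are named. Independence cannot hold either, because the third pairwise difference is fixed by the other two, and FEV1 and FVC each appear alongside their percentage form.
- *Any single p < 0.05 would satisfy every hypothesis.* Only the dose-response hypothesis uses 'and/or'.
- *All aims rank equally.* Section 1.0 ranks the objectives; it is the measures, visits and contrasts that are unranked.
- *A false result would carry into a larger trial.* The plan describes no follow-on trial and no progression rule.

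The hypotheses are also directional, so counting errors in both directions overstates false claims of benefit. That is why the working gives the one-direction figures separately.

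**Conclusion.** The point holds as a mismatch between exploratory objectives and significance-worded hypotheses, made material by an unadjusted 0.05 rule with no primary measure, visit or contrast. Its size depends on how many tests are run, which the plan leaves open. Whether a false positive is more likely than not depends on the reading: not with one group test per measure, where the chance is at most 46%, but clearly so across the full grid under moderate correlation. The independent-test figures rest on the counts above and the nominal 0.05; the correlated figures rest on assumed correlations. No reading examined brings the risk near 5%.

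**What to change.** Reword the Section 2.0 hypotheses as estimation aims. In Sections 6.0 and 17.0, replace the p < 0.05 rule with estimates and 95% confidence intervals, with no significance claim, for all measures, visits and contrasts.

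If the sponsor wants to keep a significance test, it should fix one measure before analysis, for A versus B at T4. Under Section 6.0 only A and B are randomised, while C volunteers; under Section 9.0, B is still waiting during the first four weeks. SGRQ total would suit the quality-of-life objective, but the choice is the sponsor's. A versus B after both groups have finished EA would then be reported as the dose-response estimate, with its interval and no test.

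The cost is protocol wording: no added patients or visits, and no alpha penalty. The sponsor gives up significance claims on the other measures. A retained test would be weak: with 10 per arm, a two-sided two-sample test has about 19% power for an assumed true difference of 0.5 SD and needs about 1.3 SD for 80%. That favours the estimation-only version.

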7.0 Data and Specimen Banking*

PROTOCOL TITLE: Exploring the Dose-Response Effect of Adjunctive Acupuncture on Pulmonary Rehabilitation: A Pilot Study

- NA

8.0 Sharing of Results with Subjects*

After analysis and anonymization, results will be shared with the subjects, their providers and public thought, oral presentations and written publications

9.0 Study Timelines*

The study will use a wait-time control design with varying intervention durations, i.e., dose.

Group	T0	T1	T2	T3	T4	T5	T6	T7	T8	T9
A	ACU	ACU	ACU	ACU	ACU	ACU	ACU	ACU	T7 + 3MOS	T7 + 6MOS
B	WAIT CTRL	WAIT CTRL	WAIT CTRL	WAIT CTRL	ACU	ACU	ACU	ACU		
C	CTRL	CTRL	CTRL	CTRL	CTRL	CTRL	CTRL	CTRL		

T0 will be the project start time. T4 will be 4 weeks later. T8 will be 3 months after the completion of the intervention and T9 6 months after the completion of the intervention. Patients will be assessed at T0, T4, T8, and T9 for functional and quality of life.

Current practice at the DHMC pulmonary rehabilitation unit is 6 - 12 patient per rehab cohort. Their program is applied in 4- or 8- week increments.

As this is a pilot, part of the study's purpose is to evaluate the facilitators and barriers to recruitment. For example, this protocol can be extended in time if recruitment is slow. We will be aiming for at least 10 participants per arm. If recruitment is robust, we will cap each arm at 30 participants.

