Dyspnea is a cardinal symptom of chronic obstructive pulmonary disease (COPD), and its severity and magnitude increase as the disease progresses. This can lead to significant disability and reduction on quality of life. Refractory dyspnea is a common and difficult symptom to treat in patients with advanced COPD.

Evidence supports the benefits of oral opioids, neuromuscular electrical stimulation, chest wall vibration, walking aids and pursed-lip breathing in the management of dyspnea in the individual patient with advanced COPD. Oxygen is recommended for COPD patients with resting hypoxemia, though should be reserved for patients who receive symptomatic benefit. Up until the present the evidence has been mixed to support the routine use of anxiolytic medications, nebulized opioids, acupuncture, acupressure, distractive auditory stimuli (music), relaxation, handheld fans, counselling programs or psychotherapy(1).

What is Pulmonary Rehabilitation?

Pulmonary rehabilitation is a program of education and exercise that teach patients with severe COPD how to manage breathing, increase exercise tolerance and decrease dyspnea or breathlessness. The education part of the program teaches patient how to control their breathing to pace breathing with activities, how to take medicines optimally and how best to work with your health care team. The exercise sessions are supervised by a pulmonary rehabilitation staff that prepares a personalized exercise program. Typically, exercise start at the highest tolerable level for the patient, either sitting or standing. The amount of time spent exercising and the difficulty of the exercises are slowly increased with time. As you get stronger, and develop more endurance, breathlessness reduces.

Most Pulmonary Rehabilitation programs meet two to three times a week and programs can last 4 to 12 weeks or more. Program staff constantly monitor patient progress adjusting and increasing exercise as patients are able.

PROTOCOL TITLE: Exploring the Dose-Response Effect of Adjunctive Acupuncture on Pulmonary Rehabilitation: A Pilot Study

What is Acupuncture?

Acupuncture is a method of encouraging the body to promote natural healing and to improve functioning through the application of needles and heat or other forms of energy such as electricity at specific points on the body.

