The second concern is placement. In the past, it was assumed that acupoints were precise with a variance within the range of a millimeter or 2 and anything placed further out would have no effect. Mouse models and clinical experience have shown this not to be true. That while acupoints may be the most effective locations for treatment there are often areas and zones along pathways and meridians that retain some activity even quite far from the target point, such as in the tendino-muscular meridians. As a result, there may be no part of the body that reaction free or inert.

PROTOCOL TITLE: Exploring the Dose-Response Effect of Adjunctive Acupuncture on Pulmonary Rehabilitation: A Pilot Study

The third concern is the nature of the placebo effect itself. It is unclear whether any substance or activity that can be sensed is truly inert. Some feel the placebo effect is present in every medical intervention. Sugar pills have taste and texture and all activities touching upon the mind and body convey information and have some form of meaning. Meaning evokes response which can be aligned or counter the portrayed intended purpose of the intervention.

Our innovation, in addition to promoting improved pulmonary function with the aid of acupuncture. Is to explore the dose response curve of acupuncture and use a counter or non-inert but skew control to maximize effect size. In this case, with frail patients we do not wish to sedate the lung channel, which in theory could create the greatest spread in the acupuncture effect size. Neither do we wish to choose to be near but within the same tendino-muscular plane.

Therefore, our acupuncture intervention will be EA with Lung Mu-Shu (B13, Lu2) and St 36.

Preliminary Data

Mind body medicine and acupuncture

Acupuncture by engaging in TCM and working with mind body and spirit may be consider one branch of mind body medicine. Mind-body intervention have been shown to dramatically improve health outcomes in the cardiac arena and been shown to improve both metabolic as well as immune responses. (4)

Mouse/Rat models

There has been a substantial body of research into acupuncture using mouse and rat models. Electro-acupuncture (EA) has been noted to have a variety of effects on the pulmonary function, immune response, vagal system, hormone system in these murine models of COPD.

Inflammation:

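### Across randomised groups A and B, weeks of EA and EA start time are fully aliased, so a difference at T8 or T9 cannot by itself be attributed to the amount of EA

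*Combined protocol and SAP*

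**What the plan says.** Section 9.0 makes duration the measure of dose: "The study will use a wait-time control design with varying intervention durations, i.e., dose". Section 6.0 lists group A as "INTERVENTION- 8 weeks acupuncture" and group B as "INTERVENTION- 4 week acupuncture". In the Section 9.0 timetable, A has EA in every column from T0 to T7. B is a wait control from T0 to T3 and has EA from T4 to T7. Group C has no EA.

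On timing, Section 9.0 says "T0 will be the project start time. T4 will be 4 weeks later", and for follow-up "T8 will be 3 months after the completion of the intervention and T9 6 months after the completion of the intervention". Assessments fall at T0, T4, T8 and T9, with none at T7.

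A and B are randomised. Group C consists of volunteers (Section 6.0).

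Dose response is a central aim. It is in the title, it is the second objective, and Section 3.0 gives it as the innovation ("Is to explore the dose response curve of acupuncture"). The second hypothesis in Section 2.0 reads "There will be a significant dose response relationship between adjunctive acupuncture and improvement in pulmonary function and/or quality of life". The analysis text, given in Sections 6.0 and 17.0, describes mixed models for change from baseline. It names no dose contrast and no term for when EA was given.

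**The concern.** A reader will take the 8 v 4 week comparison as the trial's test of dose. But B's four weeks are the last four of the window, so A differs from B both in having more EA and in having it earlier. Section 5.0 attaches EA to rehab sessions, and Section 3.0 says of rehab exercise in general that "The amount of time spent exercising and the difficulty of the exercises are slowly increased with time". There is thus a reason, in the plan's own account, why early and late weeks of EA might not act alike.

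At stake is what the pilot may conclude on its second objective. A difference at T8 or T9 might come from the extra weeks as such or from having EA early. No difference might mean that four more weeks add nothing wherever they are placed, or only that early weeks add nothing. Someone using the pilot to plan the length of EA in a later trial could be misled either way.

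**Working it through.** The documents give no power or sample-size figure to reproduce. The question is what the schedule can identify.

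**Inputs.** EA by week, from the Section 9.0 timetable (T0–T3 are weeks 1–4, T4–T7 are weeks 5–8). Two rehab sessions a week, from Section 25.0, which allows individual variation. I take the T8 and T9 assessments to apply to both A and B, as the Section 9.0 text does not limit them to one group.

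**Step 1: exposure.**

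| Group | EA in weeks 1–8 | Weeks | Nominal sessions | Start | End |
|---|---|---|---|---|---|
| A | 1 1 1 1 1 1 1 1 | 8 | 2 × 8 = 16 | T0 | T7 |
| B | 0 0 0 0 1 1 1 1 | 4 | 2 × 4 = 8 | T4 | T7 |
| A−B | 1 1 1 1 0 0 0 0 | 4 | 8 | | |

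B's schedule is nested in A's. The randomised difference is exactly EA in weeks 1–4, added to EA in weeks 5–8.

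**Step 2: aliasing.** Fit A and B with an intercept, weeks of EA (8, 4) and start week (0, 4). The correlation between weeks and start is −1.00, and the three-column design matrix has rank 2 at 10 or at 30 per arm. Only one of the two effects can be estimated. As an illustration, assume A−B = 0.5 SD, where A−B = 4 × (effect per week) + (early-start effect):

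- 4 × 0.125 + 0 = 0.5
- 4 × 0.0625 + 0.25 = 0.5
- 4 × 0 + 0.5 = 0.5

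All three fit equally well.

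**Step 3: what A−B estimates.** Let e be the effect at T8 or T9 of EA in weeks 1–4 and l that of EA in weeks 5–8, assumed additive. Then A = e + l, B = l, and A−B = e for any l.

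| Case | e | l | A−B | What weeks 5–8 add after an early start |
|---|---|---|---|---|
| Only early EA acts | 1 | 0 | 1 | 0 |
| Both halves act equally | 1 | 1 | 1 | 1 |
| Only late EA acts | 0 | 1 | 0 | 1 |

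So e is the gain from A's four extra weeks as scheduled, whatever l is. The assumption e = l is needed only to carry that gain over to another placement of the four weeks, such as weeks 5–8 following an early start.

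**Step 4: can other data supply l?** At T4, A has had four weeks of EA and B none, so that contrast again concerns weeks 1–4. There is no assessment at T7, and no group has EA in weeks 1–4 only. Under the additive model B−C would equal l, but C is self-selected, so B−C also carries any difference between volunteers and randomised patients.

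**Step 5: position relative to rehab.** Section 9.0 calls T0 only the project start. Sections 6.0 and 9.0 say that rehab is given in blocks of four or eight weeks; Section 25.0 says eight weeks, with individual variation. If B starts an eight-week programme at T0, its EA begins halfway through. If B's rehab instead began at T4 or lasted four weeks, EA could start with rehab in both groups, but rehab timing or amount would then differ. On neither reading does A−B isolate the amount of EA.

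**The case against.** The strongest reply is that the plan defines dose as duration and that A gets everything B gets plus four more weeks, so A−B is a randomised estimate of those four weeks. That stands. A reader might infer that the contrast is invalid, or says nothing about dose. The documents do not support that: as schedules, 8 and 4 weeks are compared fairly, and if only late EA works, finding no gain from A over B is correct for these two schedules.

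Second, some overlap is unavoidable. In a fixed eight-week window at one session frequency, a shorter unbroken course must differ in start, end or both. The plan matches the end, so time since last EA is equal in A and B at T8 and T9. A group given EA first and then stopped would differ in time since stopping instead. This stands, and it is why the schedule is not at fault.

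Third, group C provides a zero-EA level, so a reading over 0, 4 and 8 weeks is natural. It is, but it rests partly on a non-randomised comparison.

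Fourth, the plan specifies no T8/T9 A−B test of dose. A reader might infer that the trial is bound to report a false dose response; that would be conjecture. The plan does, however, predict a significant dose response, sets p < 0.05, and says nothing on how the contrast is to be read.

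Fifth, the start relative to rehab is inferred, and the statement on exercise build-up is general background rather than a description of the study programme. Both are true. The aliasing of weeks with start time does not depend on either.

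**Conclusion.** The concern holds in this form. Across A and B, duration (8 v 4 weeks) and start (T0 v T4) are completely aliased, and a larger sample does not change that. The T8/T9 difference validly estimates the effect of adding EA in weeks 1–4 to EA in weeks 5–8, with the end of EA matched. It cannot by itself be attributed to the amount of EA, and it does not show what weeks 5–8 add after an early start.

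The aliasing follows from the timetable alone. The numerical cases rest on additive effects and are illustrations. Without additivity, A−B still estimates the effect of early EA given late EA. The link to the stage of rehab is likely but not stated. This is an exploratory pilot and the remedy is wording, but it bears on a central stated aim and should be made.

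**What to change.** Leave the schedule as it is and change the text.

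1. In Sections 2.0, 6.0 and 9.0, define the T8/T9 A−B contrast as *EA throughout (T0–T7) versus EA in the second half only (T4–T7)*, estimating the added effect of EA in weeks 1–4.
2. Narrow the second hypothesis so that neither a difference nor its absence is attributed to the amount of EA alone, and list the overlap of duration and start as a limitation.
3. In the analysis text (Sections 6.0 and 17.0), label any analysis on weeks of EA (0, 4, 8) as assuming that early and late weeks act equally and, where it uses group C, as non-randomised.
4. Reconcile Sections 6.0, 9.0 and 25.0 on when rehab starts relative to T0 and how long it runs in A and B, since the reading of the contrast depends on it.

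The cost is a few sentences and a narrower dose-response claim. Allocation, visits and sample size do not change.
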